7.1.1. Prior Medications

Any medications (including vaccines) that were administered to the participant within 6 months of Screening will be considered as prior medication for this study.

Prior medication will be listed sorted by age group, dose group, participant number and summarized by dose groups using the Safety Set. They will be summarized by the generic preferred name and anatomical therapeutic chemical (ATC) class level 4. More than one ATC class per medication is possible and the medication will be reported under all applicable classes. A participant with multiple occurrences within an ATC is counted only once for that ATC class. Similarly, a participant with multiple occurrences within a generic preferred name is counted only once.

7.1.2. Concomitant Medications

Concomitant medications are defined as any medications and vaccine (other than study vaccines) taken after the study vaccine is administered and:

- Within 6 months of Screening or
- Were taken first prior to the dosing and on-going after study vaccine dose up to 6 months or
- Within 2 weeks of study vaccination for herbal products, vitamins, minerals, and over-the-counter medications.

Concomitant medications will be listed and summarized in a similar manner to that of prior medications.

For the purpose of inclusion in prior and concomitant medications tables, incomplete start and stop dates will be imputed according to the below rules (where UK, UKN, and UNKN indicate unknown or missing day, month, and year, respectively):

Missing Start Dates

If day is missing and month and year are available:

- UK-MMM-YYYY: Assume 01-MMM-YYYY (first day of the month), but if month and year are the same as the first study vaccination month and year, then assume the date of first vaccination.

If day and month are missing and year is available:

- UK-UKN-YYYY: Assume 01-JAN-YYYY (first day of the year), but if year is the same as the first study vaccination year, then assume the date of first study vaccination.

If day, month and year (date) are missing:

- UK-UKN-UNKN: Assume date of first study vaccination.

Missing Stop Dates

If day missing and month and year are available:

- UK-MMM-YYYY: Assume the last day of the month

If day and month are missing and year is available:

- UK-UKN-YYYY: Assume 31-DEC-YYYY

If day, month and year (date) are missing:

- UK-UKN-UNKN: Do not impute and assume ongoing

(Note - In case of single dose vaccine or treatment, start date may be same as that of end date.)

7.2. Study Treatments

7.2.1. Extent of Exposure and Compliance

A listing of vaccine exposure will be provided to list participants. The listing will include assigned study vaccine, actual vaccine received, date and time of the vaccination and sorted by age group, dose group and participant number.

8. Analysis of Safety and Immunogenicity Study Objectives

8.1. Analysis of Primary Safety Objective

8.1.1. Analysis of solicited local and systemic AE up to 7 days after study vaccination (day 1-7), unsolicited AEs up to 28 days after study vaccination (day 1-28), abnormal clinical safety laboratory finding up to 8 days after study vaccination (day 1-8) and non-serious Covid-19 adverse events (Day 1 – study end)

The percentages of participants with at least one solicited local or systemic AE for 7 days following vaccination (day 1-7), participants with unsolicited AEs up to 28 days after study vaccination (day 1-28), participants with abnormal clinical safety laboratory findings up to 8 days after study vaccination (day 1-8) and non-serious Covid-19 adverse events (day 1 – study end) will be computed by dose group.

8.1.2. Analysis of Medically attended Adverse Events (MAAEs), Serious Adverse Events (SAEs), and Adverse Events of Special Interest (AESIs) from study vaccination through the end of the study

Participants MAAEs and SAEs from study vaccination through the end of the study (approximately 180 days after the study vaccine administration, day 1-180) will be presented as the percentage of participants with such events throughout the study duration by dose and age group. Participants AESIs from study vaccination through the end of the study (day 1-180) will be presented by dose group.

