#### Safety Assessments:

Safety will be assessed through the collection and evaluation of solicited AEs (for 7 days, the day of vaccination and 6 subsequent days); unsolicited AEs (for 28 days after study vaccination); and MAAEs, SAEs, and AESIs for the duration of the study. Local solicited AEs will include injection site pain, redness, and swelling and localized axillary, cervical or supraclavicular swelling or tenderness ipsilateral to the vaccination arm (lymphadenopathy). Systemic solicited AEs will include fever, fatigue, headache, chills, myalgia, and arthralgia. AESIs will include virologically confirmed COVID-19 disease, pIMDs, anaphylaxis or severe hypersensitivity within 24 hours after study vaccine administration, myocarditis, and pericarditis. Safety will also be assessed based on physical examinations, vital sign measurements, and clinical safety laboratory assessments (scheduled only at screening, Day 1, and Day 8).

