**Table 2-1 Study Objectives and Endpoints**

Primary Objectives	Primary Endpoints
To evaluate the safety and tolerability of CV0501 at each dose level	
 
Percentage of participants with each solicited local and systemic AE during 7 days after vaccination (ie, the day of study vaccination and 6 subsequent days, Days 1 through 7)
 
Percentage of participants with each abnormal clinical safety laboratory finding for 8 days after study vaccination
 
Percentage of participants with unsolicited AEs for 28 days after study vaccination
 
Percentage of participants with MAAEs, AESIs and SAEs from study vaccination through the end of the study (for 180 days after the study vaccine administration), each summarized separately
 

Secondary Objectives	Secondary Endpoints
To evaluate neutralizing Ab titers against SARS-CoV-2 WT, Omicron, and Delta variants following CV0501 booster vaccination in adult participants	
 
GMTs of neutralizing Ab against pseudovirus bearing S protein from SARS-CoV-2 WT, Omicron, and Delta variants at each collection timepoint
 
GMI from baseline of neutralizing Ab titers against pseudovirus bearing S protein from SARS-CoV-2 WT, Omicron, and Delta variants at each collection time point
 

To describe seroresponse to CV0501 based on neutralizing Ab titers against pseudoviruses bearing S protein from SARS-CoV-2 WT, Omicron, and Delta variants	
 
Seroresponse rate 28 days after the booster dose (Day 29), based on neutralizing Ab titers against pseudoviruses bearing S protein from SARS-CoV-2 WT, Omicron, and Delta variants at each collection timepoint, with seroresponse defined as postboost titers <math>\geq 4\times</math> preboost titers.
 

Tertiary Objectives	Tertiary Endpoints:
CCI	

GlaxoSmithKline Biologicals SA

CV0501 Vaccine

Protocol 218595 (CV2 SARS-COV2-012 BST) Amendment 2

26 Jul 2022

CCI

[figure not shown]

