## **13 Appendices**

### **13.1 Appendix 1: Schedule of Events**

**Table 13-1** Schedule of Events

	Screening a	D1	D4	D8	D15	D29	D91	D181 (EOS)	ET Visit	Unscheduled Visit for Suspected COVID19	Unscheduled COVID-19 Convalescent Visit
Window	D-14 to -1	0	±1	±1	±3	±3	±5	±7	NA	NA	NA
Visit	1	2	Phone	3	4	5	6	7	NA	NA	NA
Informed consent	X										
Inclusion/exclusion	X										
Reassess study vaccine eligibility b		X									
Demographics	X										
Medical history (including vaccination history)	X										
Pregnancy test c	X	X									
CCI											
Physical examination f	X	X		X	X	X	X	X	X	X	X
Vital sign measurements g	X	X		X	X	X	X	X	X	X	X
Viral screening assays h	X										
Hematology and serum chemistry h	X	X d		X							
CCI											
Group assignment for Part A/ Randomization for Part B			X								
CCI											
Initiate eDiary for solicited AEs i		X									
12-lead ECG examination	X			X							
Site staff review of eDiary				X	X						
CCI											
COVID-19 assessment k									X k	X k	

Note: Due to the ongoing pandemic, safety follow-up may be completed via televisits, as permitted by country regulations.

- a. If the investigator believes there is a reasonable justification to do so, all screening procedures may be repeated (maximum 1 rescreening per participant is allowed). Only results from the rescreening visit, if it occurs, will be taken into consideration and recorded in the eCRF. The participant can only be vaccinated once the investigator receives the results and confirms the eligibility criteria.
- b. Prior to study vaccine administration, participants will be reassessed for development of any new condition that would be considered exclusionary including acute illness or pregnancy. Assessment will be based on pregnancy test results, participant-reported symptomology, vital sign measurements, and physical examination findings.
- c. A serum pregnancy test will be performed at screening in WOCBP. A urine pregnancy test by dipstick will be performed prior to study vaccination. Negative confirmation is required prior to study vaccine administration. Pregnancy test may be repeated at an unscheduled visit per investigator's discretion.
- d. On Day 1, the blood sample should be collected *before* study vaccine administration.
- e. **CCI**  
  

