3.4. Dose Adjustment/Modifications

An overdose is any dose of study vaccine given to a participant that exceeds the planned dose for an individual within a given dose group.

There is no specific treatment recommended for an overdose. Overdose itself is not to be reported as an adverse event (AE). Overdose participants will be included in the Safety Set and excluded from Per protocol Immunogenicity (PPI) Set.

4. General Statistical Considerations

Participants will be identified in the listings by the participant identification number concatenated with the site number. Data will be displayed in all listings sorted by age group, dose group and participant number.

Continuous data will be described using descriptive statistics (n, mean, standard deviation, median, minimum, and maximum).

Categorical data will be described using the participant count and percentage for each category.

For the **summary statistics** of all numerical variables unless otherwise specified, mean, confidence interval, median, standard deviation, minimum and maximum will be displayed.

A row denoted “Missing” will be included in count tabulations where specified on the shells to account for dropouts and missing values.

There is no formal hypothesis testing in this study where statistical methods are applied, the emphasis will be on estimation with 2-sided 95% Confidence intervals (CIs).

The denominator for all percentages will be the number of participants with non-missing values of corresponding parameter in that treatment within the analysis population of interest, unless otherwise specified.

A table, figure, listing (TLF) is to be generated for any required item even where no data is available or reported. In such cases, the table, figure or listing will state: “**No Data Reported**”. This will confirm to the health authorities that all data for the tables, figures, listings, and narratives are accounted for.

Baseline will be defined as the last non-missing evaluation prior to study vaccine administration, unless otherwise specified.

Study day will be calculated as follows:

- study day prior to the injection will be calculated as: date of assessment – date of the injection
- study day on or after the date of the injection will be calculated as: date of assessment – date of the injection + 1

For Safety assessment of AEs, the intervals will be calculated as follow

- solicited AEs: the day of vaccination and 6 subsequent days (day 1 through 7)

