9.2 Clinical Laboratory Evaluations

The following laboratory assessments will be performed:

Hematology:	Basophils, eosinophils, erythrocytes (red blood cells), hemoglobin, leukocytes (white blood cells), lymphocytes, monocytes, neutrophils, and platelets
Chemistry:	Alanine aminotransferase, alkaline phosphatase, aspartate aminotransferase, total and direct bilirubin, blood urea nitrogen, and creatinine
SARS-CoV-2:	
 SARS-CoV-2 serology (antibody) will include N protein for prevaccination and postvaccination timepoints. SARS-CoV-2 RT-PCR (nasopharyngeal or mid-turbinate swab)
HIV/HBV/HCV	
 Hepatitis B surface antigen test HIV 4th generation antigen/Ab test Anti-HCV Ab test (and RNA test if anti-HCV Ab positive)
Other analyses:	
Female participants of childbearing potential:
 
 β-human chorionic gonadotropin (serum test at screening; urine test at additional time points) Serum FSH, to confirm postmenopausal status

Individual safety laboratory measurements for hematology, chemistry and coagulation laboratory panel will be provided. All listings will include the cohort, study vaccine, participants ID, laboratory test name result, date and time of measurements, reference range, and flag for measurements that are outside the reference range and sorted by age group, dose group and participant number.

Laboratory abnormalities will be graded for severity using the FDA toxicity grading table (DHHS 2007). Clinically relevant laboratory abnormalities will be reported as AEs using the AE grading.

A summary of patients with an abnormal laboratory value after study vacation (up to Day 8) will be presented. An abnormal laboratory is defined as any value outside of the normal range.

A by-participant listing will be provided for pregnancy test by age group, dose group and participant number.

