15.1 Schedule of Events

	Screening ^a	D1	D4	D8	D15	D29	D91	D181 (EOS)	ET Visit	Unscheduled Visit for Suspected COVID19	Unscheduled COVID-19 Convalescent Visit
Window	D-14 to -1	0	±1	±1	±3	±3	±5	±7	NA	NA	NA
Visit	1	2	Phone	3	4	5	6	7	NA	NA	NA
Informed consent	X										
Inclusion/exclusion	X										
Reassess study vaccine eligibility ^b		X									
Demographics	X										
Medical history (including vaccination history)	X										
Pregnancy test ^c	X	X									
CCI											
Physical examination ^f	X	X		X	X	X	X	X	X	X	X
Vital sign measurements ^g	X	X		X	X	X	X	X	X	X	X
Viral screening assays ^h	X										
Hematology and serum chemistry ^h	X	X ^d		X							
CCI											
Group assignment for Part A/ Randomization for Part B		X									
CCI											
Initiate eDiary for solicited AEs ⁱ		X									
12-lead ECG examination	X			X							
Site staff review of eDiary			X	X							
CCI											
COVID-19 assessment ^k									X ^k	X ^k	

Note: Due to the ongoing pandemic, follow-up visits may be completed via telephone calls, consistent with local regulations.

- a. If the investigator believes there is a reasonable justification to do so, all screening procedures may be repeated (maximum 1 rescreening per participant is allowed). Only results from the rescreening visit, if it occurs, will be taken into consideration and recorded in the eCRF. The participant can only be vaccinated once the investigator receives the results and confirms the eligibility criteria.
- b. Prior to study vaccine administration, participants will be reassessed for development of any new condition that would be considered exclusionary including acute illness or pregnancy. Assessment will be based on pregnancy test results, participant-reported symptomology, vital sign measurements, and physical examination findings.
- c. A serum pregnancy test will be performed at screening in WOCBP. A urine pregnancy test by dipstick will be performed prior to study vaccination. Negative confirmation is required prior to study vaccine administration. Pregnancy test may be repeated at an unscheduled visit per investigator's discretion.
- d. On day 1, the blood sample should be collected *before* study vaccine administration.
- e. **CCI**
[REDACTED]
- f. A complete physical examination including height and weight will be performed at screening. Symptom-directed physical examinations will be performed as clinically indicated at subsequent visits.

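### The SAP's primary laboratory window ends at Day 8, the only scheduled post-vaccination sample may be drawn on Day 9, and no readable rule says whether it counts

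*SAP*

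**What the plan says.** **Endpoint.** Protocol Table 2-1 has as a primary endpoint the "Percentage of participants with each abnormal clinical safety laboratory finding for 8 days after study vaccination". SAP 8.1.1 implements it by reporting "participants with abnormal clinical safety laboratory findings up to 8 days after study vaccination (day 1-8". SAP 9.2 gives a second description: "A summary of patients with an abnormal laboratory value after study vacation (up to Day 8) will be presented".

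**Sampling.** The protocol synopsis lists "clinical safety laboratory assessments (scheduled only at screening, Day 1, and Day 8". The schedules of events in the protocol (Table 13-1) and in the SAP (15.1) carry the same window row, "Window D-14 to -1 0 ±1 ±1 ±3 ±3 ±5 ±7". Its entries run in the order screening, D1, D4, D8, D15, D29, D91, D181, so the Day 8 visit has ±1 day. A footnote to both schedules fixes the timing of the first on-study sample: "On Day 1, the blood sample should be collected *before* study vaccine administration".

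**Day counting.** SAP section 4 (General Statistical Considerations) says "study day on or after the date of the injection will be calculated as: date of assessment – date of the injection + 1". It also defines baseline as the last non-missing evaluation before vaccination, and uses participants with non-missing values as the general denominator for percentages.

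**The concern.** The analysis window and the visit window do not match. A site may draw the Day 8 sample one day late, fully within the protocol. That result then lies beyond the last day named in SAP 8.1.1, although it is the participant's only scheduled laboratory result after vaccination. If the table is programmed as 8.1.1 reads, valid data leave a primary safety endpoint because of a calendar label. If it is programmed by nominal visit, the same data stay in. Two competent programmers could therefore produce different primary tables from one database, and the SAP would not show which is right.

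**Working it through.** **1. Study days allowed for the post-dose sample.** Inputs are the ±1 day window (SAP 15.1, protocol Table 13-1) and the date-difference-plus-one formula (SAP section 4).

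| Draw | Elapsed days | Study day | Inside day 1-8? |
|---|---|---|---|
| One day early | 6 | 6 + 1 = 7 | yes |
| On target | 7 | 7 + 1 = 8 | yes |
| One day late | 8 | 8 + 1 = 9 | no |

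**2. The two halves of the 8.1.1 wording.** Eight elapsed days is study Day 9. SAP 8.2.2 counts this way, pairing 28 days after the booster with Day 29 and 14 days with Day 15. On that count, the verbal limit of 8 days after vaccination admits the late sample, while the parenthesis beside it does not. Other SAP text counts differently: for unsolicited AEs, section 4 and 8.1.1 equate a 28-day period with days 1 through 28. The SAP has no single convention from which the answer can be read off.

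**3. The plan's own detection figures.** Formula: P(at least one) = 1 − (1 − p)^n. The inputs and stated results are in SAP 4.1 and protocol 7.2.

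- n = 30, p = 5%: 1 − 0.95^30 = 0.7854 (stated 78.5%)
- n = 30, p = 10%: 1 − 0.90^30 = 0.9576 (stated 95.8%)
- n = 15, p = 10%: 1 − 0.90^15 = 0.7941 (stated 79.4%)

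All three reproduce. The plan states them for observing an AE; here the same formula is applied to a laboratory finding.

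**4. Effect if Day 9 samples are excluded.** The Day 9 share f is not in the documents. Assumed range: 10% to 33%, the upper end being an even spread over the three permitted days. Evaluable n = 30 × (1 − f) or 15 × (1 − f), rounded.

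| f | n of 30 | p = 5% | p = 10% | n of 15 | p = 10% |
|---|---|---|---|---|---|
| 0 | 30 | 78.5% | 95.8% | 15 | 79.4% |
| 10% | 27 | 75.0% | 94.2% | 14 | 77.1% |
| 20% | 24 | 70.8% | 92.0% | 12 | 71.8% |
| 33% | 20 | 64.2% | 87.8% | 10 | 65.1% |

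**5. Effect on the percentage.** With the non-missing denominator, an excluded participant leaves numerator and denominator together, so n falls and the percentage need not shift. Only if such participants stayed in the denominator would a true 10% rate be diluted: 0.10 × (1 − 0.10) = 9.0%, or 0.10 × (1 − 1/3) = 6.7%.

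**The case against.** **Day 8 may be a visit name.** The schedule labels the visit that way, and 9.2 reads naturally as through that visit. The SAP uses nominal days for immunogenicity visits with windows of ±3 to ±7 days, and the interval list in section 4 covers AEs only, not laboratory samples. This stands to the extent that exclusion is one reading and not a settled rule. It does not remove the problem: in 8.1.1 the laboratory range sits in the same sentence as the ranges for solicited and unsolicited AEs, which section 4 does define as calculated intervals, and nothing readable maps laboratory samples to visits.

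**The data are not lost to safety review.** Individual values are listed with out-of-range flags (SAP 9.2), and clinically relevant abnormalities are reported as AEs. Unscheduled laboratory tests are possible, so Day 8 is the only scheduled post-dose sample but not the only possible one. All of this stands and limits the consequence.

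**A stronger reading that the documents do not support.** The Day 1 sample is drawn before dosing, yet the date-only formula numbers it study day 1, inside day 1-8. A reader might infer that a participant seen on Day 9 would be classified from a pre-vaccination sample. The text says otherwise: Table 2-1, SAP 8.1.1 and SAP 9.2 all restrict findings to after vaccination, and the baseline definition makes a pre-dose Day 1 value a baseline value. What is left is a programming risk if records are selected on day number alone. It deserves a sentence because 9.2 calls any out-of-range value abnormal, with no requirement of change from baseline, and exclusion criterion 8 admits people with stable Grade 1 abnormalities.

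**Conclusion.** The point holds as a conflict between a stated analysis window and the sampling schedule. On the literal study-day reading, SAP 8.1.1 excludes a compliant Day 9 sample from a primary endpoint; on the nominal-visit reading of 9.2 it is kept; the readable text does not choose. It would go too far to say that the plan drops these samples.

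The size depends on an unknown Day 9 share. At the low end of the assumed range the loss is slight. At the high end a 30-participant cohort loses a third of its evaluable laboratory data, and detection at 5% incidence falls by 14.3 percentage points (78.5% − 64.2%). Under the section 4 denominator the harm is mainly lost precision in a descriptive study without hypothesis tests. The issue still merits correction, because the window would discard valid primary-endpoint data if programmed as written.

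**What to change.** In SAP 8.1.1 and 9.2, use one definition: the endpoint counts post-dose hematology and chemistry results from the Day 8 visit including its protocol window (study Days 7 to 9), plus any unscheduled post-dose result up to that visit. Replace the day 1-8 and up-to-Day-8 limits with it, so that the two sections agree.

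As a clarification only, add that the Day 1 pre-dose sample is baseline and does not count toward the endpoint, whatever study-day number the formula gives it.

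The cost is SAP wording and the matching record-selection rule for the laboratory table. No new data and no protocol amendment are needed.

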8.2. Analysis of Secondary Immunogenicity Endpoints

8.2.1. GMTs of neutralizing Ab titer against pseudotyped bearing S protein from SARS-CoV-2 WT, Omicron BA.1, BA.2 and BA.5 and GMI from baseline of neutralizing Ab titers against pseudotyped bearing S protein from SARS-CoV-2 WT, Omicron BA.1, BA.2 and BA.5 variants at each collection time point

For continuous variables and each dose group, summary statistics, geometric mean titer (GMT) and associated 95% CIs, and interquartile ranges will be provided. Listings will also be provided by age group, dose group, participant number and graphical presentations will be considered as needed.

Immunogenicity of the study vaccine will be assessed through GMTs at each collection time point (day 1) before the booster dose and after the booster dose (days 15, 29, 91, 181). GMTs and GMIs from baseline will be summarized with descriptive statistics including a bar chart (on log scale) for each age group versus time.

The GMT will be calculated using the following formula:

$$10^{\left\{ \frac{\sum_{i=1}^n \log_{10}(t_i)}{n} \right\}}$$

Where t_1, t_2, \dots, t_n are n observed immunogenicity titers.

The GMI measures the changes in immunogenicity titers or levels within participants (change from baseline in log titers). The GMI will be calculated using the following formula:

$$10 \left\{ \frac{\sum_{i=1}^n \log_{10} \left(\frac{v_{ij}}{v_{ik}} \right)}{n} \right\} = 10 \left\{ \frac{\sum_{i=1}^n \log_{10} (v_{ij}) - \log_{10} (v_{ik})}{n} \right\}$$

where, for n participants, v_{ij} and v_{ik} are observed immunogenicity titers for participant i at time points j and k , $k=baseline$.

Antibody titers will be summarized at baseline and each postvaccination visit (the number of participants with nonmissing data, median, minimum, maximum, GMT, and 95% CI). Geometric mean increase and the corresponding 95% CI for the GMI as well as the minimum and maximum fold-rise value will be presented by age group or prior Covid-19 infection, dose group and visit. The 95% CI will be calculated based on the t-distribution of the log-transformed fold-rise values for GMTs and GMIs, then back-transformed to the original scale for presentation.

Supporting data listings will be provided for the All Enrolled Set by age group, dose group and participant number.

Bar charts (including 95% CIs) of GMT for serum IgG and NAb antibody levels by dose, age group, prior Covid-19 infection and visit will be provided in addition to summary tables.

The GMT at each postvaccination time point, the GMI from baseline, and the 95% CIs in all cohorts will be analyzed using an ANCOVA model on log10 transformed titers with dose group and age group as fixed in the model and prior Covid-19 infection and prevaccination baseline value as covariates.

[figure not shown]
8.2.2. Seroresponse rate 28 days after the booster dose (day 29), based on neutralizing Ab titers against pseudoviruses bearing S protein from SARS-CoV-2 WT, Omicron BA.1, BA.2 and BA.5 variants at each collection timepoint, with seroresponse defined as postboost titers $\geq 4 \times$ preboost titers.

Proportion of participants with neutralizing seroresponse of serum SARS-CoV-2 WT, Omicron BA.1, BA.2 and BA.5 variants specific Ab from baseline at day 29 by dose group and prior Covid-19 infection will be tabulated with 2-sided 95% Clopper Pearson CIs. The same summaries will be generated for seroresponse rate 14 days after booster dose (Day 15) as supportive analyses.

[figure not shown]
CCI

CCI

CCI

Approved

CCI

9 Safety Analysis

Safety, tolerability, and reactogenicity will be assessed by clinical review of all relevant parameters including solicited and unsolicited AEs, SAEs, AESIs, MAAEs, AEs leading to withdrawal from study participation, safety laboratory test results, vital signs, and physical examination findings.

All safety analyses will be based on Safety Set. All safety analyses will be provided by dose group and age group unless otherwise specified.

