**Table 3-1** **Planned Cohorts, Dose Levels, Groups, and Sample Sizes for Part A**

Cohort	Vaccine	Dose Level (µg)	Group A Younger Adults $\geq 18$ to $< 65$ Years Old (n range)	Group B Older Adults $\geq 65$ Years Old (n range)	Total Cohort Sample Size
1	CV0501	12	1a (min 10; max 20)	1b (min 10; max 20)	30
2		25	2a (min 10; max 20)	2b (min 10; max 20)	30
3		50	3a (min 10; max 20)	3b (min 10; max 20)	30
4		75 or 100*	4a (min 10; max 20)	4b (min 10; max 20)	30
5		100, 150, or 200*	5a (min 10; max 20)	5b (min 10; max 20)	30

\* Depending on the reactogenicity/safety findings from groups in Cohorts 1-3, the SRT may recommend 1 of 3 prespecified dosing scenarios comprising these dose levels for groups in Cohorts 4 and 5, as described in [Section 3.1.1](#). The dose level recommendations will be made independently for Groups A (younger participants) and B (older participants).

The recruitment target will be a total of 30 participants per cohort in Cohorts 1 to 5. The 30 participants will be distributed between the younger and older age groups. A minimum of 10 participants per age group will be enrolled. A maximum of 20 participants may be enrolled in an individual age group. [CCI](#)

[REDACTED]

[REDACTED]

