### **7.5.3 Analysis of Secondary Immunogenicity Endpoints**

The secondary endpoints detailed in [Section 2](#) will be analyzed as described in the SAP. Listings will be provided, and graphical presentations will be considered as needed. In addition to descriptive statistics for continuous variables ([Section 7.5.1](#)), confidence intervals and interquartile ranges will also be provided for continuous immunogenicity variables.

Seroresponse rate with 95% CI, GMT of specific Ab with corresponding 95% CI at each timepoint and GMI from baseline of specific Ab with corresponding 95% CI at each postbaseline timepoint over pre-injection baseline will be provided by group. The GMT, the GMI, and their 95% CI in all cohorts will be analyzed using an ANCOVA with treatment and age group as fixed factors and prevaccination baseline value as a covariate.

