4.1. Sample Size

The sample size is based on clinical considerations to inform dose regimen decisions for continued clinical development.

Approximately 180 participants will be enrolled in this Phase 1 study, 5 dose-level cohorts (Cohorts 1 to 5) each comprising 2 age groups. Cohorts 6 and 7 will comprise 1 age group (younger adults). With 30 participants in each cohort, there is a 78.5% probability to observe at least 1 AE if the incidence rate is 5% and a 95.8% probability to observe at least 1 AE if the incidence rate is 10%. With 30 participants in each cohort, a 10% unevaluable rate for immunogenicity results, and a standard deviation of 0.45 for log10-transformed increase from day 1, the ratio of the upper limit of a 2-sided 95% CI and the point estimate of geometric mean increase (GMI) is 1.5. The sample size in Cohorts 6 and 7 is based on clinical feasibility rather than on statistical rationale. With 15 participants in each cohort, there is a 79.4% probability to observe at least one AE if the true incidence rate is 10%.

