4.2. Randomization, Stratification, and Blinding

Participants in Part A will be assigned sequentially to a dose-level cohort by age group. Participants in Part B will be randomly assigned on day 1 to receive study vaccine by dose-level cohort.

The study will be open label.

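### SAP 8.2.1 takes the descriptive GMT confidence interval from fold-rises, which gives no valid interval at baseline and uses the wrong SD afterwards

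*SAP*

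**What the plan says.** SAP 8.2.1 defines two statistics. The GMT is the back-transformed mean of log10 observed titers at a visit. The GMI is the back-transformed mean of within-participant log10 change from baseline.

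The section then asks for descriptive summaries: "Antibody titers will be summarized at baseline and each postvaccination visit", with the GMT and its 95% CI among the listed statistics. Protocol 7.5.3 likewise asks for "GMT of specific Ab with corresponding 95% CI at each timepoint". One interval rule serves both statistics: "The 95% CI will be calculated based on the t-distribution of the log-transformed fold-rise values for GMTs and GMIs", followed by back-transformation. No other rule for the descriptive GMT interval appears in the readable text.

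The section also plans "Bar charts (including 95% CIs) of GMT for serum IgG and NAb antibody levels by dose, age group", prior infection and visit. A model-based analysis is specified separately: "The GMT at each postvaccination time point, the GMI from baseline, and the 95% CIs in all cohorts will be analyzed using an ANCOVA" on log10 titers, with baseline titer as a covariate.

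**The concern.** The interval rule names GMTs explicitly, yet fold-rises are not the data from which a GMT is computed. At baseline the fold-rise is a constant, so the rule cannot produce the interval that the same section requires. At later visits it substitutes the spread of one variable for that of another.

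GMT at each collection timepoint is a secondary endpoint, and the trial tests no hypothesis. Protocol 7.1 puts the emphasis on estimation with 95% CIs, so the interval is the inferential output for this endpoint. Baseline precision also matters because allocation is not randomized in the main part of the study: "Participants in Part A will be assigned sequentially to a dose-level cohort by age group". A reader comparing dose groups needs to see how precisely their starting titers are known, and the stated rule would show them as known without error.

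**Working it through.** **Inputs from the documents**

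- SAP 4.1 plans with 30 per cohort, 10% unevaluable (30 × 0.9 = 27), and "a standard deviation of 0.45 for log10-transformed increase from day 1".
- Protocol 3.1: "A minimum of 10 participants per age group will be enrolled", so n = 10 is used for the smallest planned Part A age group, with no allowance for unevaluable samples.
- SAP section 4 specifies 2-sided 95% intervals.

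**Assumed, because the documents do not give it:** SD of log10 titers (s) between 0.30 and 0.70.

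**Step 1: reproduce the plan's own figure.** Upper limit / estimate = 10^(t × SD / √n). For the GMI with n = 27, t = 2.0555 and SD = 0.45, this is 10^(2.0555 × 0.45 / √27) = 1.507. The SAP states 1.5, so the planning figure is reproduced. It concerns the GMI, for which the fold-rise SD is the right one.

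**Step 2: baseline.** The log10 fold-rise of a baseline value over itself is log10(1) = 0 for every participant. The SD is therefore 0 and the ratio is 10^0 = 1.00. This needs no assumption about the titers.

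The correct ratio is 10^(t × s / √n), with t = 2.0555 at n = 27 and t = 2.2622 at n = 10:

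| Assumed titer SD | n = 27 | n = 10 |
|---|---|---|
| 0.30 | 1.314 | 1.639 |
| 0.45 | 1.507 | 2.099 |
| 0.60 | 1.727 | 2.687 |
| 0.70 | 1.892 | 3.168 |

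The ANCOVA does not fill this gap. It yields GMTs only at postvaccination visits and uses baseline as a covariate.

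**Step 3: postvaccination direction.** Write s_b and s_p for the baseline and postvaccination titer SDs and ρ for their correlation.

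Var(fold-rise) = s_p² + s_b² − 2ρ·s_p·s_b

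This equals s_p² only if s_b = 2ρ·s_p. The interval is too narrow when ρ > s_b/(2s_p) and too wide when ρ is below that. With equal SDs the switch is at ρ = 0.5.

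**Step 4: postvaccination coverage.** Take the interval as centred on the mean log titer, with its width taken from fold-rises of SD 0.45. For bivariate normal log titers, coverage = 2·T(n−1)[t × 0.45 / s] − 1, where T(n−1) is the t distribution function:

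| Assumed titer SD | n = 27 | n = 10 |
|---|---|---|
| 0.30 | 99.5% | 99.2% |
| 0.45 | 95.0% | 95.0% |
| 0.60 | 86.5% | 87.6% |
| 0.70 | 80.2% | 82.0% |

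Under the rule the typical ratio stays near 1.51 (n = 27) or 2.10 (n = 10) whatever the true titer spread.

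**Step 5: simulation.** With 100,000 replicates, n = 27, equal SDs and a fold-rise SD of 0.45, the fold-rise-based interval covered 99.3%, 95.1% and 84.3% at ρ = 0, 0.5 and 0.75. The interval built on titers covered about 95% in each case.

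**The case against.** The strongest reply is that this is a wording slip. The sentence follows directly on the GMI sentence, the GMT formula is right, and back-transforming to the original scale makes sense for a GMT only if titers were meant. A programmer may do the sensible thing, and a zero-width baseline interval would stand out in a dry-run table. That is plausible. But a program checked against the SAP must either reproduce the error or depart from the plan without record.

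Second, the coverage figures rest on one reading, an interval centred on the GMT. Read strictly, the rule gives the GMI interval itself, which at baseline is 1 to 1 on the fold-rise scale. This is fair. It makes the coverage figures conditional, but that reading gives no GMT interval at all and leads to the same correction.

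Third, the low end of the SD range is strained. If the pre and post SDs are equal, a titer SD of 0.30 with a fold-rise SD of 0.45 implies ρ = 1 − 0.2025/0.18 = −0.125, an unlikely value for a participant's own titers. An SD of 0.70 implies ρ = 1 − 0.2025/0.98 ≈ 0.79. The over-coverage end therefore deserves less weight unless the SDs differ.

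Fourth, ANCOVA intervals exist for postvaccination GMTs, and medians, ranges and interquartile ranges still show baseline spread. That limits the harm but does not supply the baseline interval the plan asks for. Redacted SAP sections and the table shells, which are not available here, might contain a different rule.

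**Conclusion.** The concern holds. As written, the rule for the descriptive GMT interval is wrong. At baseline it is degenerate by construction, whatever the data. After vaccination it is correct only if the SD of log titers happens to equal the SD of log fold-rises. The size and direction of that second error depend on titer SDs and a correlation that the documents do not give, so the coverage figures are illustrative.

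The defect is confined to the descriptive GMT tables and any GMT bar charts built on the same rule. GMT point estimates, GMI intervals, postvaccination ANCOVA intervals, Clopper-Pearson seroresponse intervals and the sample-size statement stand. No dose decision criterion in the documents uses a GMT interval. It should be corrected because it governs a secondary endpoint in an estimation-only trial, but it does not threaten the study's main conclusions.

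**What to change.** Replace the interval sentence in SAP 8.2.1 with wording such as:

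> The 95% CI for the GMT is based on the t-distribution of the log10-transformed titers at that visit, and the 95% CI for the GMI on the t-distribution of the log10-transformed fold-rises at postvaccination visits; both are back-transformed.

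Then check that the GMT table and bar-chart programs follow it, including the baseline row and the age-group and prior-infection breakdowns, and correct them if they do not. The cost is one sentence and a program check. No new data are needed, and the design does not change.
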